4.4 Outcome measures

The primary endpoint is the 24 h-proteinuria reduction between arms as suggested by Inker LA et al (44). It will be assessed after 4 and 8 months in the ACiGaN study and after 10 months in the CHRONiGaN trial.

The secondary end point is the GFR slope calculated as the mean of individual slope obtained from individual linear regression of eGFR overtime (3 years). Based on the International Consensus definition of clinical trial outcomes for kidney failure (23) we have also considered other secondary end points listed below.

Primary and secondary end points that will be evaluated in the two RCTs are listed below:

Primary endpoint:

- Between-arms difference in proteinuria reduction within 4 and 8 months in ACiGaN and within 10 months in CHRONiGaN study.

Secondary endpoints:

- eGFR slope calculated as mean of individual slope obtained from individual linear regression of eGFR overtime (3 years);
- eGFR decline > 40 % from the baseline value;
- composite end point: GFR decline > 40%, ESKD (defined as long-term GFR \leq 15 ml/min/1.73m² for more than three months or need for maintenance dialysis or kidney transplantation) or death due to kidney disease;
- absolute difference between last GFR value and baseline GFR;
- stable renal function defined as a decline in GFR \leq 5 ml/min/1.73m² at the end of three years follow-up;
- mean annual change in the slope of the reciprocal of serum creatinine concentration;
- time-averaged proteinuria (TA-P) calculated as the weighted mean of all post-randomization measurement, with weights representing the time elapsed since the previous measurement;
- proteinuria slope, calculated as a mean of individual slope, obtained from individual linear regression of daily proteinuria overtime (3 years);
- complete remission of proteinuria defined as achievement of urinary protein level \leq 0.2 g/day or a urinary protein-to-creatinine ratio \leq 0.2 g/g;
- partial remission of proteinuria defined as achievement of a urinary protein reduction \geq 50% or greater compared with baseline value.

The end points will be evaluated monthly in IgAN patients with active renal lesions in the first eight months after kidney biopsy and then every three months. In IgAN patients with chronic or moderate renal lesions the end points will be evaluated every three months in the first two years after the enrollment and then every six months.

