4.5 Participant timeline

Total Study duration: approximately 6 years:

- Enrollment period: 3 years
- Treatment and Follow-up period: 3 years + 30 days.

Figure 2A and **2B** illustrate the time schedule of enrollment, interventions, assessments and visits for participants.

Figure 2A. SPIRIT 2013 STATEMENT OF THE ACiGAN STUDY: Time schedule of the enrolment, interventions, assessments and visits of the participants.

Time point	STUDY PERIOD																			
	Enrolment	Allocation	Post-allocation														End of Treatment	End of Study		
			t ₁	t ₂	t ₄	t ₆	t ₈	t ₁₂	t ₁₅	t ₁₈	t ₂₁	t ₂₄	t ₂₇	t ₃₀	t ₃₃	t ₃₆				
	- t ₁	t ₀															t ₃₆	30 days after last treatment		
Enrolment:																				
Eligibility screen	x																			
Informed consent	x																			
Kidney biopsy	x																			
Laboratory data	x																			
Allocation		x																		
Interventions:																				
(A) Cs+RASBs (4 months) → RASBs			●	—————														●		
(B) RASBs (4 months) →Cs+RASBs (4 months)→RASBs			●	—————														●		
Assessments:																				
Serum creatinine	x		x	x	x	x	x	x	x	x	x	x	x	x	x	x	x			
eGFR	x		x	x	x	x	x	x	x	x	x	x	x	x	x	x	x			
Daily proteinuria	x		x	x	x	x	x	x	x	x	x	x	x	x	x	x	x			
Adverse events	x		x	x	x	x	x	x	x	x	x	x	x	x	x	x	x		x	
Concomitant medications	x		x	x	x	x	x	x	x	x	x	x	x	x	x	x	x		x	
Outcome variables:																				
Proteinuria reduction (primary end point)						x	x	x	x	x	x	x	x	x	x	x	x	x		
eGFR slope reduction (secondary end point)			x	x	x	x	x	x	x	x	x	x	x	x	x	x	x	x		
Biological samples collection		x	x	x	x	x	x	x				x				x				

Figure 2B. SPIRIT 2013 STATEMENT OF THE CHRONIGAN STUDY: Time Schedule of the enrolment interventions, assessments and visits of the participants.

Time point	STUDY PERIOD															
	Enrolment	Allocation	Post-allocation												End of Treatment	End of Study
	- t ₁	t ₀	t ₁	t ₄	t ₈	t ₁₀	t ₁₂	t ₁₄	t ₁₈	t ₂₄	t ₂₇	t ₃₀	t ₃₃	t ₃₆	t ₃₆	30 days after last treatment
Enrolment:																
Eligibility screen	x															
Informed consent	x															
Kidney biopsy	x															
Laboratory data	x															
Allocation		x														
Interventions:																
(A) RASBs (4 months)→ Dapagliflozin +RASBs			●	—————											●	
(B) RASBs (4 months)→ Cs+RASBs(6 months)→RASBs			●	—————											●	
Assessments:																
Serum creatinine	x		x	x	x	x	x	x	x	x	x	x	x	x		
eGFR	x		x	x	x	x	x	x	x	x	x	x	x	x		
Daily proteinuria	x		x	x	x	x	x	x	x	x	x	x	x	x		

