4.7 End of Study and Patient withdraw

The end of the study is defined as the last visit of the last enrolled subject.

A visit of end of study will be performed 30 days after last treatment to collect data about any adverse events and other administered therapies.

The withdraw of enrolled patients from study treatment and/or from the whole study will be done in the following conditions:

- withdraw of the informed consent
- pregnancy
- superimposed malignant diseases
- kidney failure (end-stage kidney disease)
- dialysis
- renal transplant
- non-compliance with study procedures
- Investigator judgment, for any ethical, medical, or scientific reasons
- Death.

The patient may withdraw from the treatment/trial, at any time, without penalty or loss of benefits to which he/she is otherwise entitled.

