6.5 Analysis populations

The primary trial efficacy analysis will be done in the intention-to-treat (ITT) population, including all randomly assigned participants.

A secondary analysis will be performed in the persistent population (PP, i.e. including all patients who persisted on the investigational drugs for at least 4 and 8 months (ACiGaN trial) or 10 months (CHRONiGaN trial).

Patients who need to change their study treatment prior to 1st month (ACiGaN trial) or 4 months (CHRONiGaN trial) will be considered as dropouts.

The safety population will be represented by all patients receiving at least one dose of the investigational drugs.

A recent systematic review (15) evidenced that patients with histological lesion M1 were responsive to corticosteroids. Therefore, we will do a subgroup analysis to evaluate the effect of corticosteroids in active and chronic IgAN patients with lesion M1 versus M0.

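### The secondary endpoint of last GFR minus baseline has no time point, so unequal withdrawal between the open-label arms can bias it, in a direction that depends on why patients leave

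*Protocol*

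**What the plan says.** Protocol section 4.4 and the Synopsis (Endpoints) list among the secondary endpoints the "absolute difference between last GFR value and baseline GFR". No reading time is attached. Neighbouring endpoints do have one: the eGFR slope is taken over 3 years, and the next entry, "stable renal function defined as a decline in GFR" of at most 5 ml/min/1.73 m², is read "at the end of three years follow-up". The secondary objective in section 2.2 is the effect on renal function and kidney damage at 3 years.

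Section 4.5 gives each patient the same planned course ("Treatment and Follow-up period: 3 years + 30 days"), and Figures 2A and 2B schedule eGFR up to month 36.

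Section 4.7 foresees departures before then: "The withdraw of enrolled patients from study treatment and/or from the whole study will be done in the following conditions". The list includes withdrawn consent, pregnancy, malignancy, non-compliance and "Investigator judgment, for any ethical, medical, or scientific reasons", as well as kidney failure, dialysis, renal transplant and death. Patients may also leave at any time of their own accord. The section does not say which reasons end treatment only and which end follow-up, or whether GFR is still collected afterwards.

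Section 6.4 plans a secondary analysis of repeated eGFR measurements by linear mixed models or GEE. ESKD and death due to kidney disease are counted in the composite endpoint of section 4.4.

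**The concern.** A last-value endpoint measures two things at once: how fast GFR changes and how long the patient was observed. Where GFR falls over time, a patient last seen at month 6 has had less time to lose function than a completer with the same disease. In an open-label trial, where investigator judgment and non-compliance are grounds for withdrawal, the arms need not leave at the same rate, at the same time or for the same reasons. The contrast can then show a difference that treatment did not cause, or hide one that it did, and it no longer answers a question about renal function at 3 years.

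This is not a complaint about an absent missing-data rule, which a statistical analysis plan could supply. The protocol itself fixes the reading as the last value, and an analysis plan would be expected to follow that definition.

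A smaller, related point concerns stable renal function. It needs a 3-year value, and section 4.7 allows patients who reach ESKD, dialysis or transplant to leave the whole study without one. Section 4.4 does not say how they are classed.

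**Working it through.** **Plan's own figure.** The protocol gives no size, slope or power for either GFR endpoint. Its only powered figure is the ACIgAN sample size on proteinuria (section 6: difference 0.6, SD 1.0 g/24 h, two-sided 0.05, power 90%, 10% dropout). It reproduces: 2 × (1.960 + 1.282)² × 1.0² / 0.6² = 58.4, so 59 per arm; 59 / 0.90 = 65.6, so 66 per arm and 132 in total. It does not bear on the point below.

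**Inputs.** Reading time (last value) from section 4.4, full follow-up of 36 months from section 4.5, and the possibility of leaving from section 4.7. The slopes, withdrawal rates, leaving times and ESKD fall used below are assumptions and are not in the protocol.

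**Step 1: leaving unrelated to GFR, same true slope in both arms.** With loss s per year, a proportion p leaving at time t years and the rest read at 3 years:

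mean change = −3s + p × s × (3 − t)

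The spurious difference between arms is (p₁ − p₂) × s × (3 − t). With 25% versus 10% leaving at month 6 (t = 0.5):

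| Loss per year | Completer loss | Leaver loss | Arm with 10% leaving | Arm with 25% leaving | Spurious difference |
|---|---|---|---|---|---|
| 3 | 9 | 1.5 | −9 + 0.10 × 7.5 = −8.25 | −9 + 0.25 × 7.5 = −7.125 | 1.125 |
| 5 | 15 | 2.5 | −15 + 0.10 × 12.5 = −13.75 | −15 + 0.25 × 12.5 = −11.875 | 1.875 |

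The arm with more leavers appears better by 1.1 to 1.9 ml/min/1.73 m². Read at month 36 for everyone, the difference is 0.

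**Step 2: milder patterns.** With leaving spread evenly over the three years (mean 1.5 years), 15% versus 5% gives 0.10 × 1.5 × s, which is 0.15 to 0.75 for losses of 1 to 5 per year. At 30% versus 10% it gives 0.20 × 1.5 × s, which is 0.30 to 1.50. With 10% in both arms and the same timing, it gives 0.

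**Step 3: masking a true difference.** With losses of 3.3 versus 3.0 per year, the true 3-year deficit is 0.9. With 30% versus 10% leaving evenly over time, the last-value means are −3.3 × (3 − 0.45) = −8.415 and −3.0 × (3 − 0.15) = −8.55. The worse arm then appears better by 0.135.

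**Step 4: leaving because of ESKD.** Assume such a patient falls from 50 to 15, a change of −35 carried as the last value. An arm with 5 percentage points more of these patients differs by 0.05 × (−35 + 3s): −1.6, −1.3 and −1.0 for s = 1, 3 and 5. The sign is the reverse of Step 1. Part of this is a real difference in outcome, but it is still read before month 36, and it shows that the direction is not fixed.

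**Step 5: stable renal function, if ESKD leavers were left out.** Take 150 per arm (the CHRONIgAN size), 75 truly stable in each, and 10% versus 2% withdrawn with ESKD. Leaving them out gives 75/135 = 55.6% versus 75/147 = 51.0%, favouring the arm with more ESKD. Counting them as not stable gives 50% versus 50%.

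**The case against.** Several counter-arguments carry weight.

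- **Direction.** A reader might infer that the arm with more early withdrawals always looks better. The protocol does not support that. Section 4.7 lists kidney failure, dialysis and transplant alongside reasons unrelated to GFR, and those patients carry a low last value (Step 4). This stands: the sign depends on why patients leave.
- **Size.** No slope, imbalance or timing comes from the protocol. Its only dropout figure is 10% for each trial, with no difference between arms. Having 25% of one arm leave around month 6 is an unfavourable case. Section 6.1 plans separate acute, chronic and total eGFR slopes, so linear loss from baseline is itself a simplification. This stands: the figures are illustrations.
- **Stable renal function.** A reader might infer that ESKD patients certainly have no 3-year value and drop out of the denominator. Section 4.7 says treatment and/or study, so some may stay in follow-up, and nothing says that they are excluded. By the definitions they cannot be stable: entry requires at least 30, ESKD by GFR is at most 15, and that fall of at least 15 exceeds the allowance of 5. Handling may also sit in an analysis plan that is not shown. The Step 5 example further presumes a difference in ESKD, which is itself a renal outcome. This half therefore stands only as a clarification.
- **Consequence.** Section 4.4 names the GFR slope as the secondary endpoint and introduces the rest as additional. The composite and the repeated-measures models also cover renal function. This limits the damage, but neither changes how the last-value endpoint is defined.

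Intention-to-treat does not remove the problem. Section 6.5 states: "The primary trial efficacy analysis will be done in the intention-to-treat (ITT) population, including all randomly assigned participants". Including everyone does not help when each patient is read at a different time.

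**Conclusion.** The point holds for the last-value endpoint. As defined, it compares patients at different follow-up times, does not match the 3-year objective, and can be biased when withdrawal differs between arms. The direction cannot be stated in advance. Under assumed equal slopes of 3 to 5 ml/min/1.73 m² per year and 10% versus 25% leaving at month 6, the spurious difference is 1.1 to 1.9 ml/min/1.73 m², or 22.5% to 37.5% of the protocol's own 5 ml/min/1.73 m² stability threshold. It is smaller under milder assumptions and zero when withdrawal is equal and similarly timed.

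For stable renal function no error is shown. The protocol leaves open how patients who reach kidney failure and leave the study are classed, and one sentence would settle it.

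The primary endpoints are unaffected. The change is worth making because it is cheap and the present wording is a firm instruction rather than a gap.

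**What to change.** In section 4.4 and the Synopsis, replace the last-value endpoint with change in eGFR from baseline to month 36, estimated in all randomised patients from all scheduled visits with a repeated-measures mixed model. Section 6.4 already plans a linear mixed model or GEE, so the protocol needs to name the mixed model for this endpoint. The mixed model is preferable because ordinary unweighted GEE needs the stronger assumption that data are missing completely at random. State how eGFR after dialysis, transplant or death is handled, since anchoring at month 36 does not settle that by itself.

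As a clarification, define stable renal function over all randomised patients and count ESKD, dialysis, transplant or death due to kidney disease before month 36 as not stable. Sections 4.4 and 4.7 should also be reconciled on whether eGFR is still collected after a patient leaves treatment.

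The cost is a rewording of two secondary endpoints and slightly more analysis work. eGFR is already scheduled to month 36, so no visits or measurements are added.

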1.2. Rationale

In our CLlIgAN study, we have planned to evaluate:

- (i) The effect of early start corticosteroid therapy combined with RASBs (experimental arm) versus RASBs alone in IgAN patients with active renal lesions (AClIgAN) who will receive corticosteroids after 4 months of RASBs (standard care) in presence of persistent proteinuria ≥ 0.5 g/24 hours and eGFR ≥ 30 ml/min/1.73 m² (control arm).
- (ii) The effect of SGLT2i (dapagliflozin) combined with RASBs (experimental arm) versus corticosteroids combined with RASBs (control arm) in IgAN patients with chronic or moderate renal lesions (CHRONlIgAN) after a run-in phase of 4 months in which they will receive RASB therapy alone (standard care).

In both studies patients enrolled in the control arms will be treated according to the evidence-based recommendations (standard care) provided within the KDIGO guidelines.

In conclusion, we would like to evaluate the effect of early start corticosteroids in IgAN patients with active renal lesions (AClIgAN) and to spare corticosteroids therapy in IgAN with chronic or moderate renal lesions (CHRONlIgAN) administering Dapagliflozin.

We would also provide earlier ESKD risk prediction by using our tool DialCheck (32).

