To our knowledge, this is the first study in which corticosteroids are administered immediately after the kidney biopsy in IgAN patients with active renal lesions. Based on the existing evidence from randomized clinical trials, the KDIGO guidelines suggest in those cases: RASBs for 3-6 months and then corticosteroids in presence of persistent proteinuria and $GFR >30$ ml/min/1.73 m². This therapeutic approach, although supported by evidence, may be a challenge based on empiric clinical knowledge supported also by findings of cohort studies. This demonstrates that after 3-6 months active renal lesions become chronic and consequently no association may be found between exposure to corticosteroids and clinical response for IgAN patients. In our randomized clinical study we compare the standard approach proposed by KDIGO guidelines (RASBs for 3-6 months followed by corticosteroids) vs a novel approach consisting of early corticosteroid therapy combined with RASBs from the beginning.

CHRONIgAN TRIAL

Patients with chronic (T1,2) or moderate renal lesions (M0,1; S0,1, E0, C0, T0) will be enrolled in a two-arm trial with 1:1 allocation ratio to compare Dapagliflozin combined with RASBs (experimental arm) versus corticosteroids combined with RASBs (control arm) after 4 run-in months of RASBs treatment. The enrolled patients will have proteinuria ≥ 0.5 g/day and GFR ≥ 30 ml/min/1.73 m².

Participants will receive study treatments by 4 weeks from the kidney biopsy.

Patients assigned to the experimental arm will receive RASBs therapy (4 run-in months) followed by Dapagliflozin (10 mg /day orally) combined with RASBs for a total of 32 consecutive months. Patients assigned to the control arm will receive RASBs therapy (4 run-in months) followed by oral corticosteroids therapy (prednisone) for six months (0.4 mg/kg body weight for 2 months and then gradual reduction of 5 mg/day for 4 months) and then RASBs alone for a total of 36 consecutive months.

This is a parallel group, two arm, superiority trial with 1:1 allocation ratio.

Rationale of the study design

We decided the combination Dapagliflozin and RASBs because recently, SGLT2is were administered in patients with type 2 diabetes and in other participants with CKD (some of them were affected by IgAN) (29-31). In these studies, the effect of SGLT2is was compared with a placebo.

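### In CHRONiGaN, time-averaged proteinuria gives about 8% to 11% of its weight to run-in months in which both arms are assigned the same treatment, which shrinks the expected difference between arms.

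*Protocol*

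**What the plan says.** Section 4.4 (Outcome measures) lists, for both trials, "time-averaged proteinuria (TA-P) calculated as the weighted mean of all post-randomization measurement", "with weights representing the time elapsed since the previous measurement". The synopsis gives the same definition. No start time is set for CHRONiGaN.

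Section 1.2 describes the CHRONiGaN comparison as coming "after a run-in phase of 4 months in which they will receive RASB therapy alone (standard care", and section 3 places it "after 4 run-in months of RASBs treatment". Section 3 then gives the sequence in each arm:
- Experimental: "Patients assigned to the experimental arm will receive RASBs therapy (4 run-in months) followed by Dapagliflozin", the combination lasting "combined with RASBs for a total of 32 consecutive months".
- Control: "Patients assigned to the control arm will receive RASBs therapy (4 run-in months) followed by oral corticosteroids therapy".

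Sections 6.2 and 8.3 randomise the patient once consent is signed. Figure 2B puts allocation at t0 and shows the 4 months of RASBs as the first post-allocation step in both arms. It schedules daily proteinuria at enrolment and at months 1, 4, 8, 10, 12, 14, 18, 24, 27, 30, 33 and 36. Section 4.5 sets the overall length: "Treatment and Follow-up period: 3 years + 30 days".

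**The concern.** As written, the months called a run-in fall after randomisation. A mean of all post-randomisation values therefore includes a stretch in which the two arms are assigned the same drugs. Those months add weight to the average but no expected difference between arms, so the endpoint is pulled toward zero by its definition.

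The problem is specific to CHRONiGaN. One definition serves both trials, and in ACiGaN the assigned treatments differ from the start. What is at stake is the size and precision of the TA-P comparison in a superiority trial whose sample of 300 is described in section 6 as opportunistic.

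**Working it through.** **Is there a plan figure to reproduce?** Not for CHRONiGaN. Section 6 gives 150 per arm without an effect, an SD or a power. The only derived sample size is ACiGaN's, and it does reproduce: a difference of 0.6, SD 1.0, two-sided 0.05 and 90% power give 59 per arm, or 66 after 10% dropout, 132 in all.

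**Weight on the run-in, Figure 2B visits.** Each weight is the time since the previous visit, counted from t0:

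| Visit (month) | 1 | 4 | 8 | 10 | 12 | 14 | 18 | 24 | 27 | 30 | 33 | 36 |
|---|---|---|---|---|---|---|---|---|---|---|---|---|
| Weight | 1 | 3 | 4 | 2 | 2 | 2 | 4 | 6 | 3 | 3 | 3 | 3 |

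- Run-in share = (1 + 3)/36 = 11.1%.
- Assume no expected difference up to month 4. Then the full TA-P difference is (32/36) × the difference over months 4 to 36, which is 0.889 of it.
- The factor depends only on the weights. Constant, waning and sign-changing effects after month 4 all gave 0.889.

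**Sensitivity of the share**
- Section 4.4 schedule (every three months for two years, then every six): only the month-3 value falls in the run-in. Share 3/36 = 8.3%, factor 33/36 = 0.917.
- Figure 2B with no weight on the first visit: 3/35 = 8.6%.
- Shorter follow-up on Figure 2B visits: 4/30 = 13.3%, 4/24 = 16.7%, 4/18 = 22.2%, 4/12 = 33.3%.

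**Illustrative cost in patients (assumptions, not plan figures).** The sample-size factor is (36/32)² × Var(full TA-P)/Var(TA-P after month 4). With equal variance at each visit and a common within-patient correlation ρ, Var is proportional to ρ + (1 − ρ)S, where S is the sum of squared normalised weights:
- Full: S = 126/36² = 0.0972.
- After month 4: S = 116/32² = 0.1133.

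| ρ (assumed) | Variance ratio | Sample-size factor |
|---|---|---|
| 0 | 0.0972/0.1133 = 0.858 | 1.266 × 0.858 = 1.09 |
| 0.5 | 0.5486/0.5566 = 0.986 | 1.25 |
| 1 (SD unchanged) | 1 | 1.27 |

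If the correlation decays with time instead (0.3 to 0.7 at six months apart), the factor is 1.13 to 1.19. On the section 4.4 schedule the common-correlation range is lower: 1.07 at ρ = 0, and (36/33)² = 1.19 at unchanged SD. In all these cases the smaller SD of the longer average does not make up for the smaller difference. None of them includes a gain from covariate adjustment.

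**The case against.** **Counting from randomisation is the natural intention-to-treat choice.** It compares the arms as whole sequences, is conservative for superiority and does not inflate type I error. This is right: the current definition is a legitimate estimand. It answers a diluted question, though, since the primary objective in section 2.1 concerns dapagliflozin with RASBs against corticosteroids with RASBs.

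**A later window loses patients.** Sections 6.4 and 6.5 analyse everyone randomised, and section 6.5 foresees CHRONiGaN dropouts before month 4. This stands as a cost. The same patients already lack a value for the primary endpoint, which section 4.4 places at month 10.

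**The root problem is where randomisation sits.** If it were moved to after the run-in, the existing wording would already exclude these months and the point would vanish. That is correct, and the point depends on allocation at t0.

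**Stronger readings that the protocol does not support**
- A reader might quote power falling from 90% to 82%, or from 80% to 70%. CHRONiGaN has no stated power to fall from, and those drops also need an unchanged SD.
- A reader might say that no difference at all can arise before month 4. The trial is open label, so only the assigned drugs are known to be the same.
- For that reason month 4 should not be treated as a baseline. It is measured after allocation, when knowledge of the arm could already have influenced care.
- A reader might extend the point to the proteinuria and eGFR slopes. The 4/36 weight does not apply to a regression slope, and section 6.1 already plans acute, chronic and total eGFR slopes.

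**Conclusion.** The point holds for TA-P in CHRONiGaN, with modest consequence. With allocation at t0, full 36-month follow-up and no expected difference during the run-in, the definition keeps only about 0.89 (Figure 2B visits) to 0.92 (section 4.4 schedule) of the difference over months 4 to 36, and less where follow-up is cut short. The loss of power cannot be fixed from the protocol. Roughly 9% to 27% more patients is an illustration on the Figure 2B visits, and 27% is reached only if the SD is unchanged. The primary endpoint is not affected, and TA-P is one of ten secondary endpoints.

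**What to change.** For CHRONiGaN, add to section 4.4 and the synopsis that TA-P is the time-weighted mean of measurements taken after month 4 up to month 36, with the between-arm comparison adjusted for the enrolment (pre-randomisation) proteinuria value. Keep the mean of all post-randomisation values as a sensitivity analysis. On the Figure 2B visits the run-in weight becomes zero, and the expected difference is 36/32 = 1.125 times that under the current definition.

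State how patients lost before month 4 enter the intention-to-treat analysis, because they will have no observed value. Reconcile the Figure 2B visits with the section 4.4 schedule, because the weights depend on which applies.

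The cost is a sentence or two of protocol text and no extra visits: Figure 2B already schedules the enrolment value and the later measurements. If randomisation is moved to after the run-in, the new window is unnecessary.
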